### **Research Question and Objectives**

Primary objective:

Effectiveness assessment of Lunaphil Ultra

Secondary objectives:

Effectiveness and safety assessment of Lunaphil Ultra

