## 5 Rationale and Background

Skin aging is a complex and multifactorial process resulting in various functional and aesthetic changes in the skin (1). It is an inevitable process that can be described clinically as features of wrinkles, sun spots, uneven skin color, and sagging skin (2). Additional clinical findings include tear trough, a drop of the angle of the mouth, loss of definition in the mandibular border, platysmal bands, evident veins, and NLFs as one of the typical clinical manifestations of facial aging (3).

The perception of health and age is a critical aspect in the common judgment of attractiveness and people are judged to be less attractive as they age (4). Attractiveness influences both self-perception and social behavior and is related to traits such as self-confidence and social acceptance. Therefore, aesthetic interventions can improve psychological well-being and quality of life (5).

Dermal fillers are widely used for the correction of deep wrinkles, including NLFs. Treatments with dermal fillers provide favorable aesthetic outcomes with minimal invasiveness and no downtime following surgical procedures (6). Hyaluronic acid (HA) fillers, the most popular dermal fillers (7), demonstrate desirable effects on the fibroblast phenotype, including higher cell proliferation and type I collagen synthesis (8). HA fillers have predictable efficacy, a good safety profile, quick recovery, and simplicity in administration (9, 10).

Different factors, including HA concentration, polymer chain length, and crosslinking degree or technology, influence filler properties such as the requisite needle size, particle size, duration, extrusion force, and elastic Modulus (G'). All of these factors will critically influence product selection and indication (11). Among these factors, crosslinking is essential to slowing down the enzymatic degradation rate of the HA by endogenous hyaluronidase and prolonging the product's half-life. The extent of crosslinking strongly impacts the biophysical and biological properties of a filler, including tissue integration, water uptake, resistance to degradation, and filler biocompatibility and consequently might have clinical implications (12).

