In an equivalence test of means using two one-sided tests on data from a paired design, a sample size of 97 achieved 80% power at a 2.5% significance level. When the true difference between the means was 0.000, the standard deviation of the paired differences was 0.510, and the equivalence limits were -0.170 and 0.170. Considering a drop-out rate of 10%, total sample size required is 108.

Study Population Criteria

Inclusion Criteria

1. Subjects \geq 30 years of age

2. Visible bilateral NLFs that are approximately symmetrical and have an equal severity ranging from moderate to severe (assessed at the deepest part)
3. Able to follow study instructions and likely to complete all required visits
4. Signed informed consent

Exclusion Criteria

1. History of bleeding disorders or participants receiving or recently exposed (≤ 3 weeks) to continuous treatment with thrombolytics, anticoagulants, platelet inhibitors, or NSAIDs
2. Acute herpetic eruption
3. Known susceptibility to keloid formation, hypertrophic scarring or clinically significant skin pigmentation disorders
4. Known sensitivity to local anesthetics of the amide type (such as lidocaine), history of hypersensitivity to gram-positive bacterial proteins, history of multiple severe allergies, history of anaphylactic shock
5. Known hypersensitivity to any component of the study products or excipients (like hyaluronic acid)
6. History of receiving immune therapy or a history of autoimmune disease
7. History of active chronic debilitating systemic disease
8. History of connective tissue disease, history of malignancy (except for non-melanoma skin cancer) within the last 5 years
9. Clinically significant active dermatologic disorders within the last 6 months
10. Use of oral retinoids, OTC or prescription antiwrinkle treatments, microdermabrasion, or chemical peels in the NLF area within the last 4 weeks or intention to use them during the study
11. Any prior cosmetic procedure or tissue augmentation at the NLF injection site within 1 year before study entry (or intent to undergo such a procedure during the study)
12. Pregnancy or breastfeeding

Withdrawal Criteria

1. Withdrawal of consent by the participant
2. Noncompliance, including refusal of study medical requirements, refusal of procedures as stated in the study protocol, or use of prohibited medications
3. The occurrence of an undesirable event that causes the investigator to consider the participant's exclusion from the study

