Descriptive statistics for baseline characteristics will be presented as mean and standard deviation for continuous variables, and as frequency and percentage for categorical variables.

Section 7: Statistical Analysis

This section describes the planned statistical analyses for efficacy and safety outcomes. Results will be summarized using appropriate descriptive statistics and analyzed using suitable statistical models depending on the data type. Treatment effects will be presented with 95% confidence intervals and two-sided p-values, using a significance level of 0.05.

Primary Endpoint Analysis

For the statistical analysis of the primary outcome (equivalence assessment of the mean level of improvement from baseline in NLFs severity score), both categories of Per-Protocol and Intention-to-Treat statistical population will be examined. Although the main approach is the results of the statistical analysis of the Per-Protocol population, eventually a sensitivity analysis will be performed between the results of the said analysis and the results of the statistical analysis of the Intention-to-Treat population.

Paired t-test or a signed-rank test will be used to compare the mean level of improvement from baseline in NLFs severity score based on assessments by evaluating investigators between Lunaphil Ultra (Hyaluronic acid, produced by Espad Pharmed Co.) compared to Juvéderm® Ultra 4 (Hyaluronic acid, produced by Allergan Co.). The 95% confidence interval (CI) for the mean difference between the two treatments will be calculated. Equivalence will be concluded if the entire 95% CI falls within the pre-specified equivalence margin of ± 0.17 .

Secondary Endpoints Analysis

- The number of patients with improvement score for the PGAIS will be analyzed using a McNemar test.
- The proportion of NLFs maintaining a clinically significant improvement will be analyzed using a McNemar test.
- Injection volume to obtain optimal result will be analyzed with a paired t-test or a signed-rank test.

The number of NLFs receiving touch-up treatment will be analyzed using a McNemar test.

Safety Analysis

All adverse events (AEs) data will be descriptively analyzed. Also, AEs in two groups are compared

using Pearson chi-square test.

The incidence and percentage of treatment-emergent adverse events will be reported, categorized by system organ class (SOC) and preferred term (PT). Adverse events' severity, seriousness, and causality assessment will be reported.

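### The week-24 equivalence rule uses only the difference between products, so it can be met with no improvement left in either fold

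*SAP*

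**What the plan says.** The protocol abstract (Research Question and Objectives) gives the primary objective as "Effectiveness assessment of Lunaphil Ultra". SAP Section 5 makes it comparative: equivalence of efficacy against the reference filler, measured by mean improvement from baseline in WSRS at week 24.

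SAP Section 7 then plans a paired t-test or signed-rank test between products, with a 95% CI for their mean difference. The decision follows: "Equivalence will be concluded if the entire 95% CI falls within the pre-specified equivalence margin of ± 0.17". No minimum improvement is set for either product.

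The sample size paragraph (Protocol 8.6 and the SAP) states that "a sample size of 97 achieved 80% power at a 2.5% significance level". Its other inputs are a zero true difference, a paired SD of 0.510 and limits of ±0.170. It assumes no absolute improvement for either product.

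Four other parts of the plan matter here:
- Every participant has both folds treated, one with each product (Protocol abstract, Setting). No fold is untreated.
- The two folds must be of equal severity at entry (Protocol 8.2.1, Inclusion Criteria).
- Folds with a reduction of at least 1 point, and PGAIS improvement, are week-24 secondary outcomes. Both are tested by McNemar (SAP Section 7).
- Descriptive summaries are promised in Protocol 8.7.1 and in the opening of SAP Section 7.

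**The concern.** An equivalence rule based on a difference cannot separate two products that both still work from two products that have both stopped working. A trial often handles this with an untreated control, or with a stated expectation of how much effect the reference should show. This plan has neither. Because the folds start equal, a full return to baseline on both sides gives an expected difference of exactly 0, which is the value the trial is powered for.

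The planned tests do not close the gap. McNemar uses only participants whose two folds disagree, so it is also null when both folds fail.

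At stake is the wording of the main conclusion. Equivalent effectiveness at week 24 could be declared under the pre-specified rule with no effectiveness shown for either product.

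**Working it through.** **Inputs from the documents.** Evaluable pairs n = 97; SD of paired differences 0.510; margin ±0.170; true difference 0; 2.5% per one-sided test, which matches a 95% CI; drop-out 10%.

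**Step 1: reproduce the plan's sample size.**
- Normal approximation to power: 2Φ(0.17 × √97 / 0.51 − 1.960) − 1 = 2Φ(3.283 − 1.960) − 1 = 2Φ(1.323) − 1 ≈ 0.814.
- With the t distribution, integrating over the sample SD: 79.7% at n = 96 and 80.3% at n = 97. So 97 is the smallest n that reaches 80%.
- Drop-out: 97 / 0.9 = 107.8, rounded up to 108.

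The plan's figures are correct.

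**Step 2: does remaining improvement enter the rule?** Write each fold's improvement as a common mean μ plus its own deviation. The paired difference is (μ + e1) − (μ + e2) = e1 − e2, so μ cancels. Simulation of the rule (n = 97, SD 0.51, true difference 0, normal data, 20,000 runs each) agrees:

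| Mean improvement in both folds | Rule met |
|---|---|
| 0 | 80.0% |
| 0.5 | 79.9% |
| 1.0 | 80.1% |
| 1.5 | 79.9% |

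At an observed SD of 0.51 the CI half-width is 1.985 × 0.51 / √97 = 0.103. The rule is then met whenever the observed difference is within 0.17 − 0.103 = 0.067 of zero.

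**Step 3: what if the SD is not 0.51?** The documents give no other value, so these are assumptions. With true difference 0 and n = 97:

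| Assumed SD of paired difference | Rule met |
|---|---|
| 0.30 | nearly 100% |
| 0.40 | 97% |
| 0.51 (plan) | 80% |
| 0.58 | 63% |
| 0.63 | 49% |
| 0.71 | 29% |

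The SD would be small if nearly all folds were back at the same grade. It could be larger than planned while folds are losing grades at different times. The pass rate could therefore move either way during waning.

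**Step 4: add a condition on each product.** Require also that the lower 95% limit of mean improvement be above 0 in both folds. The documents give no SD for change within a fold, so 0.5 to 1.0 is assumed, with the paired SD held at 0.51. Chance of meeting both conditions at true difference 0:

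| Mean improvement | SD 0.5 | SD 0.75 | SD 1.0 |
|---|---|---|---|
| 0 | about 1% or less | about 1% | about 1% |
| 0.3 | 80% | 77% | 64% |
| 0.5 | 80% | 80% | 80% |

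**The case against.** **Loss of effect would be visible anyway.** This is the strongest point, and it stands as far as reporting goes. The secondary outcome is itself a proportion of folds keeping a reduction of at least 1 point, and descriptive summaries are promised. If both fillers had worn off, the tables would show it. But no within-product interval is named, and a table does not change a pre-specified conclusion. The gap is in the decision rule.

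**The objective is comparative, so an equivalence conclusion answers it.** The SAP wording supports this, and reliance on the reference product's effect is a general limit of active-controlled equivalence trials. It would carry more weight if the plan stated what week-24 improvement is expected of the reference. It does not.

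**A change from baseline is uncontrolled.** True. Regression to the mean after selecting moderate or severe folds, and assessors knowing that both folds were treated, could each produce apparent improvement. The added condition is also a low bar: at an assumed SD of 0.62 the half-width is 0.125, so an observed mean of 0.13 points would pass. It can block an empty claim but cannot prove effect.

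**Stronger readings that a reader might infer, and that the documents do not support:**
- *That the rule will be met if both fillers fail.* It can be met, with probability about 80% at the planning SD.
- *That it gets easier to pass as the effect wanes.* Step 3 shows this depends on SDs that the documents do not give.
- *That the plan errs if an early 0.30-point difference shrinks to 0.10 by week 24.* The endpoint is the week-24 difference, and 0.10 lies inside ±0.17.
- *That the protocol expects wear-off by week 24.* Its background says that "crosslinking is essential to slowing down the enzymatic degradation rate of the HA by endogenous hyaluronidase and prolonging the product's half-life". It gives no duration.

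**Conclusion.** The point holds as a gap in the decision rule. With the plan's own inputs (97 pairs, SD 0.51, true difference 0), the rule is met about 80% of the time whatever improvement remains, including none. No planned test or condition concerns improvement within a product. That result follows from the form of the rule; only the 80% depends on the planning SD.

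The documents do not show that loss of effect by week 24 is likely, and the sample size is correct and unaffected. The figures for the added condition rest on an assumed within-fold SD of 0.5 to 1.0 and on normal data. The change should be made, because the stated conclusion can otherwise be reached without any evidence of retained effect.

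**What to change.** In SAP Section 7:
1. Pre-specify, for each product, the mean WSRS improvement from baseline at week 24 and the proportion of folds with a reduction of at least 1 point, each with a 95% CI.
2. Conclude equivalence of effectiveness only if the 95% CI of the difference lies within ±0.17 and the lower 95% limit of mean improvement is above 0 for both products.
3. Otherwise, if only the first part is met, report no difference between products, with retained effect not shown at week 24.
4. State that the second part is a minimum safeguard, because there is no untreated fold.

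The same paired difference at earlier WSRS visits is optional support only. Both folds may be retreated towards optimal correction at week 2, which pulls early differences towards zero.

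**Cost.** SAP wording and summary tables from data already collected, with no change to the 108 participants. Essentially no power is lost at a mean improvement of 0.5 or more. At a mean of 0.3, power is about 80%, 77% or 64% for an assumed within-fold SD of 0.5, 0.75 or 1.0. The sponsor also accepts that the claim is lost if improvement has not been retained.

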### ***8.7.2 Main Statistical Methods***

The mean level of improvement from baseline in NLFs severity score based on assessments by evaluating investigators and the injection volume to obtain optimal result will be analyzed using either a paired t-test or a signed-rank test.

The number of patients with an improved score for the PGAIS, proportion of NLFs with clinically significant improvement and the number of NLFs receiving touch-up treatment will be analyzed using a McNemar test.

The safety data will be analyzed primarily using summary statistics. Summary statistics are included the number of subjects (number and percentages) and then classified according to system organ class and preferred term for AEs and SAEs. The incidence of the preferred term for grades 3 and 4 of AEs will be reported. Moreover, causality will be assessed and its results will be reported by frequency and percentage.

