	
Two treatments will be allowed over a 2-week period (initial treatment plus one touch-up) to achieve optimal correction of the NLFs. The level of correction will be assessed by the evaluating investigator at week 2 after the initial treatment and, if less than optimal, the treating investigator will be directed to retreat the undercorrected NLF(s).

Outcomes	
Efficacy and safety outcomes
 
Primary outcome:
 
Mean level of improvement from baseline in NLF severity score by WSRS (wrinkle severity rating scale) at 24 weeks
 
Secondary outcomes:
 
• Number of subjects with improvement score for the 5-point Physician Global Aesthetic Improvement Scale (PGAIS) at 24 weeks• Proportion of NLFs maintaining a clinically significant improvement in NLF severity score (≥ 1-point reduction from baseline) at 24 weeks• Volume to Obtain Optimal Cosmetic Result (Initial Treatment + Touch-up)• Number of NLFs receiving touch-up treatment• Incidence of adverse events (Injection Site Reactions) and incidence of adverse events (Injection Site Reactions) based on severity
Statistical Plan	
Processes of cleaning, inspecting, and transforming will be done in the procedure of data analysis. Also, the descriptive analysis will be performed using frequency and percentage, average and standard deviation regarding the type of the variables.
 
Primary Endpoint:
 
The mean level of improvement from baseline in NLFs severity score based on assessments by evaluating investigators will be analyzed using a paired t-test or a signed-rank test.
 
Secondary Endpoint:
 
The number of patients with improvement score for the PGAIS will be

	
analyzed using a McNemar test.
 
The proportion of NLFs with clinically significant improvement will be analyzed using a McNemar test.
 
Injection volume to obtain optimal result will be analyzed with a paired t-test or a signed-rank test.
 
The number of NLFs receiving touch-up treatment will be analyzed using a McNemar test.
 
Safety:
 
The safety data will be analyzed primarily using summary statistics. The incidence, frequency, and severity of adverse events (Injection Site Reactions) will be reported.

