The main outcome of this study is the evaluation of the equivalency of the efficacy of Lunaphil Ultra (Hyaluronic acid, produced by Espad Pharmed Co.) compared to Juvéderm® Ultra 4 (Hyaluronic acid, produced by Allergan Co.), which is measured by evaluate the mean level of improvement from baseline in NLF severity score by WSRS at week 24.

Secondary Outcomes

Evaluating the effectiveness of Lunaphil Ultra (Hyaluronic acid, produced by Espad Pharmed Co.) compared to Juvéderm® Ultra 4 (Hyaluronic acid, produced by Allergan Co.) in the following criteria:

- The number of participants with improved score in Physician Global Aesthetic Improvement Scale (PGAIS) at week 24 compared to baseline which was assessed by two evaluators
- The proportion of NLFs that sustained a clinically meaningful reduction in severity score (≥ 1 -point reduction from baseline) at week 24
- The injected volume to obtain optimal aesthetic result (initial treatment + touch-up)
- The number of NLFs receiving touch-up treatment

Safety outcome

The incidence, severity and causal relationship of adverse events will be reported. The intensity of AEs will be graded according to the CTCAE v5.0, and terminology for AEs will be chosen according to the MedDRA system organ class and preferred term (MedDRA Desktop Browser 4.0 Beta). Seriousness will be also recorded for all AEs.

Section 6: Descriptive statistics

[figure not shown]
Participant flow

The flow of participants throughout the study is planned to be summarized. A participant flow diagram will illustrate the number of subjects at each stage of the study, including:

- Number of subjects randomized to each treatment group
- Number of subjects who received at least one dose of study treatment
- Number of subjects who completed the study and those who discontinued (with reasons)
- Number of subjects included in each analysis set (PP, ITT, Safety)

Tabulations of participant disposition will also be provided, including counts and percentages by treatment arm. The reasons for exclusion from each analysis set will be documented in the subject listings and summarized in the Clinical Study Report (CSR).

All flow and disposition data will be based on the data recorded in the clinical database up to the date of database lock.

Baseline characteristics

Baseline characteristics	Categories
Age	-
Sex	Male/Female
History of filler injection in NLF	Yes/No
WSRS	1 to 5

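### The five-point PGAIS is compared between products only as improved versus not improved, which costs sensitivity that a paired analysis of all five levels would keep

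*SAP*

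**What the plan says.** The SAP Synopsis (Outcomes) lists first among the secondary outcomes: "Number of subjects with improvement score for the 5-point Physician Global Aesthetic Improvement Scale (PGAIS) at 24 weeks". SAP Section 7, Secondary Endpoints Analysis, gives the method: "The number of patients with improvement score for the PGAIS will be analyzed using a McNemar test". Protocol section 8.7.2 assigns the same test to "The number of patients with an improved score for the PGAIS". SAP Section 5 adds that the score is "compared to baseline which was assessed by two evaluators". Neither document says which of the five points count as improved, or how two evaluators' ratings become one value.

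No analysis of the five PGAIS levels is planned. WSRS, which the SAP's baseline table lists as 1 to 5, gets two analyses in Section 7: a paired comparison of improvement on the full scale, and a McNemar test of the proportion of folds improving by at least one point.

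No power, expected rate, discordance or margin is stated for PGAIS. The equivalence rule in Section 7 (95% CI inside ±0.17) is written for the primary WSRS endpoint only. For effects in general, Section 7 says: "Treatment effects will be presented with 95% confidence intervals and two-sided p-values, using a significance level of 0.05".

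**The concern.** McNemar's test uses only the pairs in which one fold is improved and the other is not. If most folds are still improved at week 24, few pairs are discordant. A product that moves folds from a higher to a lower grade, both counted as improved, adds nothing to the test statistic. The ratings that would show such a shift are already recorded, but no planned analysis uses them.

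In an equivalence trial, insensitivity in a supporting outcome is not neutral. In a superiority trial a weak test works against the sponsor. Here a non-significant secondary result can look like agreement with the primary conclusion. At stake is how much the PGAIS result can tell a reader, not the validity of the primary test.

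**Working it through.** **The plan's own sample size.** SAP Section 3 states that "a sample size of 97 achieved 80% power at a 2.5% significance level", with the further inputs that "the standard deviation of the paired differences was 0.510, and the equivalence limits were -0.170 and 0.170". For a paired two one-sided test with true difference 0, the normal approximation gives

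n = [SD × (z₀.₉₇₅ + z₀.₉₀) / margin]² = [0.51 × (1.960 + 1.282) / 0.17]² ≈ 94.6, so 95.

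Exact t-based power is 79.7% at 96 pairs and 80.3% at 97, so 97 is confirmed. Then 97 / 0.9 = 107.8, which agrees with "Considering a drop-out rate of 10%, total sample size required is 108". This calculation concerns WSRS only. I use its 97 evaluable pairs below.

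**McNemar power in terms of improved rates.** Exact two-sided test at 0.05, 97 pairs, with total discordance assumed to be 10% to 30%:

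- 5-point difference in improved rates: 10% to 23%.
- 10-point difference: 36% to 93%.
- 15-point difference (discordance 15% to 30%): 73% to 99.8%.

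Power is therefore low for small differences and adequate for large ones. No single figure describes it.

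**Binary against five-level analysis.** Assumptions, none taken from the documents:

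- Each fold has its own PGAIS rating, as a McNemar comparison of products implies.
- Paired latent scores are bivariate normal and cut into five categories.
- The top three categories count as improved, and the reference product's improved folds are spread evenly over them.
- One product is worse by 0.3 SD on the latent scale.

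The table shows 3,000 simulated trials of 97 pairs per row (simulation standard error at most √(0.25/3000) = 0.9 points).

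| Reference improved | Other product improved | Correlation | Discordant pairs | McNemar exact | McNemar asymptotic | Signed-rank, five levels |
|---|---|---|---|---|---|---|
| 70% | 59% | 0.5 | 31 | 43% | 51% | 74% |
| 70% | 59% | 0.7 | 24 | 54% | 64% | 91% |
| 80% | 71% | 0.5 | 26 | 35% | 44% | 74% |
| 80% | 71% | 0.7 | 20 | 45% | 55% | 89% |
| 90% | 84% | 0.5 | 17 | 23% | 31% | 72% |
| 90% | 84% | 0.7 | 13 | 28% | 37% | 89% |
| 95% | 91% | 0.5 | 10 | 14% | 21% | 74% |
| 95% | 91% | 0.7 | 8 | 15% | 24% | 87% |

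A paired t-test on the five levels agreed with the signed-rank test within 2 points in a separate run.

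The last row can be followed by hand. With 8 discordant pairs, a 7–1 split gives p = 2 × 9/256 = 0.070, so only 8–0 is significant (p = 2/256 = 0.008). The expected excess is about 97 × (0.950 − 0.911) = 3.8 pairs, a split near 6–2.

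**Other shifts,** over the same rates and correlations:

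- 0.2 SD: exact McNemar 6% to 24%, asymptotic 11% to 32%, signed-rank 39% to 59%.
- 0.4 SD: exact 27% to 80%, asymptotic 36% to 86%, signed-rank 93% to 99%.
- No shift: signed-rank rejects in about 5% of runs and exact McNemar in 1% to 3%. The five-level gain is not bought with false positives.

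**The case against.** The strongest reply is that the endpoint is a binary count wherever it is defined, and McNemar is the standard test for paired binary data. That stands: the test is not wrong, and the binary endpoint should stay.

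Second, the documents attach no equivalence conclusion to PGAIS. A reader might infer that a non-significant McNemar result is meant to support equivalence. No passage says so. The only such rule is the WSRS interval against ±0.17, and Section 7 promises 95% CIs, which would make imprecision visible. This stands too, although an interval for the difference in improved rates still cannot show shifts among improved grades.

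Third, the primary analysis already looks for graded differences. A 0.3 SD shift at correlation 0.7 is a paired standardised difference of 0.3 / √(2 × 0.3) = 0.39, or about 0.32 to 0.34 after cutting into five categories. The primary margin is 0.17 / 0.51 = 0.33 in the same units. If WSRS shifted as much as PGAIS, equivalence would be concluded in only about 1% to 4% of trials. So a quiet PGAIS result beside a wrong equivalence claim would be uncommon unless the two scales diverge. This limits the importance of the point but does not remove it, since a separate scale is useful precisely because it may diverge.

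Fourth, a reader might conclude that McNemar simply has little power here. The documents cannot support that: computed exact power runs from about 10% to over 99% across plausible differences and discordances. Nor is a shift always invisible to it. In the scenarios above the improved rate does fall. Only movement confined to the grades above the cut is lost entirely.

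Last, a signed-rank p-value would also be a difference test without a margin. This stands, and it is why the interval should be the main addition.

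**Conclusion.** The concern holds as a loss of sensitivity in a secondary outcome. In every simulated scenario with a real shift, the improved/not comparison had less power than the paired five-level analysis, and the gap was widest when nearly all folds improved. At a 0.3 SD shift it was about 14% to 54% (exact) or 21% to 64% (asymptotic) against 72% to 91%. These figures rest on assumed improvement rates, correlation, shift, category cuts and per-fold rating; the documents supply only the number of pairs and the significance level.

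It is not an error in the equivalence rule, and McNemar is not invalid for the endpoint as defined. The point is a cheap improvement, not a necessary correction.

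**What to change.** Keep the improved/not count and its McNemar test as the stated endpoint. Add one line to SAP Section 7: a paired analysis of the five-point PGAIS per fold at week 24, reported as the mean between-fold difference with a 95% CI, with a signed-rank test as a check. This gives PGAIS the same pair of analyses that WSRS already has.

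In the same edit, state which points count as improved and how the two evaluators' ratings are combined, since both analyses depend on a single value per fold. State also that a non-significant PGAIS result will not be interpreted as equivalence; a formal equivalence statement on PGAIS would need its own justified margin.

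No new data are needed. The cost is one more secondary result in a plan without multiplicity adjustment. If the data have already been unblinded, label the added analysis post hoc.
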